## 15.2 Accuracy of automatic measurements (Part 2)

In order to establish the baseline inter- and intra-observer variability, the original rater group (ORG) consisting of three board certified cardiologists analyzed 58 2D TTE studies, repeating the measurements twice. This generated six values for each measurement in each study. The new rater group (NRG) consisting of a fourth cardiologist (FC) and Ligence Heart performed measurements in the same 58 studies. NRG performance was evaluated by calculating the number of measurements of each type that were in the limits of variation. FC was used as the performance benchmark for Ligence Heart.

There was no significant difference in variation between Ligence Heart and FC ( $p > 0.05$ ) and Ligence Heart had non-inferior accuracy to FC for all automatic measurements (**Table 3**). The lowest number of studies in agreement with ORG was 93.1% in RAA and 94.55% in RVM for Ligence Heart and FC, respectively. For AoS, STJ, IVSd, LVEDD, LVESD, LVESV4A and RVOTPD both FC and Ligence Heart were in agreement with ORG for 100% of studies. Ligence Heart discarded 2-4 studies in RAMAD, LAV4A, LVEDV4A, LVESV4A, LVEDV2A, LVESV2A, RVEDA and RVESA due to insufficient quality scores of automatic predictions (**Table 3**). Ligence Heart confidence interval for the number of studies in agreement with ORG intersected FC for all automatic measurements (**Figure 1**) and comparing each measurement between FC and Ligence Heart yielded a median Pearson correlation R 0.74 (IQR 0.59-0.83) (**Figure 2**).

Comparison of correlation between all raters and NRG measurement relation to ORG measurements is visualized in **Supplementary figures 1 and 2**, respectively.

**Table 3.** Comparison of Ligence Heart and cardiologist agreement with original rater group.

Measurement	Ligence Heart studies in agreement with ORG (95% CI)	FC studies in agreement with ORG (95% CI)	P-value*	N studies	N studies not passing confidence filter in Ligence Heart	Pass
RAMAD	96.3 ± 5.03	98.15 ± 3.59	0.56	54	4	Yes
AoA	98.28 ± 3.35	98.28 ± 3.35	1	58	0	Yes
AoS	100.0 ± 0.0	100.0 ± 0.0		58	0	Yes
STJ	100.0 ± 0.0	100.0 ± 0.0		58	0	Yes
AAo	98.28 ± 3.35	100.0 ± 0.0	0.32	58	0	Yes
LAD	94.83 ± 5.7	100.0 ± 0.0	0.08	58	0	Yes
LAV4A	98.21 ± 3.47	94.64 ± 5.9	0.31	56	2	Yes
IVSd	100.0 ± 0.0	100.0 ± 0.0		58	0	Yes
LVPWd	96.55 ± 4.7	100.0 ± 0.0	0.16	58	0	Yes
LVEDD	100.0 ± 0.0	100.0 ± 0.0		58	0	Yes
LVESD	100.0 ± 0.0	100.0 ± 0.0		58	0	Yes
LVEDV4A	98.21 ± 3.47	100.0 ± 0.0	0.32	56	2	Yes
LVESV4A	100.0 ± 0.0	100.0 ± 0.0		56	2	Yes
LVEDV2A	96.3 ± 5.03	100.0 ± 0.0	0.16	54	4	Yes

UAB Ligence	Clinical Investigation Report	2021-04-09
		Rev: 1.0

[figure not shown]
LVESV2A	96.3 ± 5.03	100.0 ± 0.0	0.16	54	4	Yes
RAA	94.44 ± 6.11	98.15 ± 3.59	0.31	54	4	Yes
RVB	98.18 ± 3.53	98.18 ± 3.53	1	55	3	Yes
RVM	100.0 ± 0.0	94.55 ± 6.0	0.08	55	3	Yes
RVOTPD	100.0 ± 0.0	100.0 ± 0.0		58	0	Yes
RVEDA	98.18 ± 3.53	100.0 ± 0.0	0.32	55	3	Yes
RVESA	98.18 ± 3.53	100.0 ± 0.0	0.32	55	3	Yes

*ORG - original rater group consisting of three board certified cardiologists; FC – fourth board certified cardiologist. \*P values for measurements that fall 100% in agreement in both groups are undefined. The “Pass” column specifies whether measurement accuracy is considered to be non-inferior. In order for the automated measurements to pass, a P value of > 0.05 or undefined is required which means that there is no significant difference in variation between Ligence Heart and FC measurements.*

UAB Ligence	Clinical Investigation Report	2021-04-09
		Rev: 1.0

[figure not shown]
Figure 1. Comparison of LigenceHeart and cardiologist measurements in agreement with the original rater group

**Figure 1.** The X axis represents the number of studies that were measured in agreement with ORG by Ligence Heart or FC. Each Y axis position represents a different measurement. 95% CIs are shown for Ligence Heart only. Ligence Heart 95% CI lower bound is at or above FC performance. ORG - original rater group. FC - fourth cardiologist.

[figure not shown]
UAB Ligence	Technical file	2021-04-09
		Rev: 1.0

Supplementary figure 1. Correlation of measurements between all raters

Electronic version of the document is valid, printed version of the document is not controlled. The document is stored at: Ligence Cloud storage unit. Internal company document.

UAB Ligence	Clinical Investigation Report	2021-04-09
		Rev: 1.0

[figure not shown]

**Supplementary figure 1.** Pearson correlation coefficients between all raters is shown. A value of -1 is assigned whenever the correlation is not calculated, either because it would be a duplicate or because it would compare measurements with the same rater and run. OR - original rater, R1 and R2 - run 1 and run 2, FC - fourth cardiologist, LH - Ligence Heart. Run 1 and run 2 refers to different repeats of the study by the same rater.

[figure not shown]

UAB Ligence	Clinical Investigation Report	2021-04-09
		Rev: 1.0

Figure 2. Correlation of measurements between FC and Ligence Heart

[figure not shown]
UAB Ligence	Clinical Investigation Report	2021-04-09
		Rev: 1.0

**Figure 2.** Correlation between Ligence Heart and FC for different measurements. The values in X and Y axes correspond to the units that are used for that measurement, e.g. millimeters for LVEDD. R is calculated using Pearson correlation. FC - fourth cardiologist.

[figure not shown]
UAB Ligence	Technical file	2021-04-09
		Rev: 1.0

Supplementary figure 2. Comparison of measurements between original rater group and new raters

[figure not shown]

Electronic version of the document is valid, printed version of the document is not controlled. The document is stored at: Ligence Cloud storage unit. Internal company document.

UAB Ligence	Clinical Investigation Report	2021-04-09
		Rev: 1.0

[figure not shown]

UAB Ligence	Clinical Investigation Report	2021-04-09
		Rev: 1.0

UAB Ligence	Clinical Investigation Report	2021-04-09
		Rev: 1.0

**Supplementary figure 2.** All individual measurements from ORG and NRG visualized. Each row represents a different study, grey dots represent values from run 1 and run 2 performed by the ORG. Orange and blue diamonds show the FC and Ligence Heart measurements, respectively. Run 1 and run 2 refers to different repeats of the study by the same rater. ORG - original rater group. NRG - new rater group.

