## 12.5 Automatic Measurements Analysis (Part 2)

### 12.5.1 Statistical Methods Values and Characteristics

**Two-way ANOVA** – test used to detect any overall differences between related means.

ANOVA characteristics

UAB Ligence	Clinical Investigation Report	2021-04-09
		Rev: 1.0

Source of variation	Degrees of Freedom	Mean Square
Patient	n - 1	MSS
Cardiologist	t - 1	MSR
Error (Patient x Cardiologist)	(n - 1)(t - 1)	MSSR
Error (Cardiologist)	nt(m - 1)	MSE

ANOVA variance components

Estimates of Variance Components
$\hat{\sigma}_S^2 = \frac{MSS - MSE}{mt}$
$\hat{\sigma}_R^2 = \frac{MSR - MSSR}{mn}$
$\hat{\sigma}_{SR}^2 = \frac{MSSR - MSE}{m}$
$\hat{\sigma}_e^2 = MSE$

**Standard Error of Measurement** – a measure of how much same measurements made by different physicians are spread around a “true” score. SEM in Two-way repeated measures ANOVA includes both the variability among raters’ measurements and within raters’ measurements.

$$SEM = \sqrt{\frac{MSR + (n - 1)MSSR + n(m - 1)MSE}{mn}}$$

**Minimal Detectable Change** – minimal amount of change that is required to distinguish a true change from a change due to variability of measurement or random error. MDC is derived from SEM and calculated as confidence interval. In this analysis 95% confidence interval will be used.

$$MDC_{95} = 1.96 * \sqrt{2}SEM$$

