## 12.5.2 Data analysis

Two-way ANOVA will be employed in this analysis to prepare for further investigation. Inter-rater reliability and SEM will be calculated from the results of ANOVA. SEM will be used to get minimal detectable change. Absolute difference between the automated system measurement and mean of the raters’ measurements will be compared with MDC as the primary endpoint of the analysis to check if there is a significant difference between physicians and automated system. The same difference will be compared with SEM as the secondary endpoint. Same analysis will be conducted with measurements of the 4th rater. Results will allow to compare the accuracy of automated systems measurements and physicians’ measurements.

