### 16.2 Automatic functionalities (Part 2)

Due to the fact that echocardiography is prone to considerable inter- and intra-observer variability, it was important to perform comparison of the automatic measurements using data from multiple board certified cardiologists. The first three cardiologists established the acceptable intra- and inter-observer variation ranges while the fourth cardiologist and Ligence Heart were used as independent raters with accuracy calculated as the number of times measurements fell within acceptable variation range in the selected studies. Non-inferiority of automatic measurements accuracy to a cardiologist was established by conducting the t-test and assuring p-values are  $> 0.05$  which proves that any differences are non-significant. All of the measurements passed the required performance threshold, and for 7 out of 21 automatic measurements, both Ligence Heart and FC had full agreement with the ORG.

Conversely, Ligence Heart automatic functionalities did not return a value for at least one study in 11 measurements, however, there was a sufficient number of studies for all measurements where automatic analysis value was returned to ensure statistical power. The reason for no value being returned in a particular study has to do with the automatic predictions not passing quality thresholds which are employed in each step of the automatic functionalities (classification, cardiac phase or cycle detection and measurement prediction confidence). This ensures that a lower number of false values is provided to the user of the medical device and serves as a safety mechanism by reducing the number of potential false positive findings.

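### Part 2 turns each continuous reading error into in or out of a wide limit and passes a measurement when a t-test on those 0/1 values gives p > 0.05 or is undefined, so a device with 1.5 times a cardiologist's error SD would pass about 60% of the time per measurement

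*Protocol*

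**What the plan says.** Section 12.5.2 takes the absolute difference between the automated reading and the raters' mean, and says the difference "will be compared with MDC as the primary endpoint of the analysis to check if there is a significant difference" between physicians and the automated system. The fourth rater's readings get the same analysis. Section 12.5.1 defines the limit as "MDC_{95} = 1.96 * \sqrt{2}SEM", and says that SEM "includes both the variability among raters’ measurements and within raters’ measurements". A second cut-off is planned: "The same difference will be compared with SEM as the secondary endpoint".

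Section 15.2 then reports shares: "NRG performance was evaluated by calculating the number of measurements of each type that were in the limits of variation". It does not name the limit. Section 16.2 describes "accuracy calculated as the number of times measurements fell within acceptable variation range in the selected studies" and says that non-inferiority was established by a t-test with p above 0.05. The footnote to Table 3 gives the pass rule as p above 0.05 or undefined, per measurement. No margin is stated.

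**The concern.** For every study the investigation holds the actual distance of Ligence Heart and of the fourth cardiologist from the three raters' mean. The test keeps only whether each distance is below the limit. An error just under 2.77 SEM counts the same as no error, so only the extreme tail can separate the two readers. The footnote to Table 3 reads the result as showing no difference in variation, but variation is never compared; only tail counts are. Section 5.2.1 names accuracy, variance and error rate as what is to be compared.

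At stake is hypothesis 2 in 12.1 (non-inferior accuracy), which 16.2 declares shown for a pre-market device. With few events and a pass rule that rewards a non-significant result, a less precise device can pass for lack of information.

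**Working it through.** **1. Table 3 counts.** Percentages times N give whole numbers. (The text of 15.2 gives 93.1% for RAA where Table 3 has 94.44%; Table 3 is used.)
- Sum of N: 10×58 + 3×56 + 4×55 + 4×54 = 580 + 168 + 220 + 216 = 1,184 per reader, 2,368 in all.
- Out of limits, Ligence Heart: RAMAD 2, AoA 1, AAo 1, LAD 3, LAV4A 1, LVPWd 2, LVEDV4A 1, LVEDV2A 2, LVESV2A 2, RAA 3, RVB 1, RVEDA 1, RVESA 1 = 21 (1.8%).
- Out of limits, fourth cardiologist: RAMAD 1, AoA 1, LAV4A 3, RAA 1, RVB 1, RVM 3 = 10 (0.8%).
- Total 31/2,368 = 1.3%. Seven measurements have no event, hence no p-value, and are marked as passing. The other 14 have 1 to 4 events each.

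**2. Reproducing the stated p-values.** A two-sample t-test on the 0/1 values reproduces all 14. For LAD, 3/58 against 0/58, p = 0.08. With 58 studies and no cardiologist reading out, the device fails only from 4 out; with 1 cardiologist reading out, only from 7.

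**3. Size of the limit.** 1.96 × √2 = 2.77. Because SEM holds between- and within-rater variance, a single cardiologist reading has error SD of about 1 SEM. The raters' mean rests on three raters with two runs each ("This generated six values for each measurement in each study"). Its error variance v is therefore between SEM²/6 (all variance from repeats) and SEM²/3 (all between raters). With an assumed split of 10% rater, 40% patient-by-rater and 50% repeat, v = 0.5/3 + 0.5/6 = 0.25 SEM².

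**4. Chance of falling outside, SD ratio 1.5, v = 0.25.**
- Cardiologist: SD √(1 + 0.25) = 1.118; 2.77/1.118 = 2.48; about 1.3% out, or 0.8 of 58.
- Device: SD √(2.25 + 0.25) = 1.581; 2.77/1.581 = 1.75; about 8% out, or 4.6 of 58.

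The expected device count sits close to the failure threshold, hence the high pass rate.

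**5. Simulated pass rates.** Assumptions: normal unbiased errors, 58 studies, limit 2.77 SEM, pass if two-sided p > 0.05 or undefined, one measurement.

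| Device SD / cardiologist SD | In/out t-test | Paired t-test on absolute errors |
|---|---|---|
| 1.25 | about 90% | about 73% |
| 1.5 | about 60% | about 33% |
| 1.75 | about 26% | about 10% |

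At ratio 1.5, letting v run from 1/6 to 1/3 SEM² gives 59–62% and 29–37%. If the limit is instead set so that the cardiologist is inside 99.2% of the time, as Table 3 shows, the in/out rate is 53–71%. The planned SEM cut-off still passes 47–64%. The gain comes from dropping the cut-off rather than from pairing: a paired test on the in/out values still passes about 58–61%. A Wilcoxon test on absolute errors gains less (37–44%).

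**6. With a margin.** Using a 95% CI for the ratio of mean absolute errors and an assumed margin of 1.5, power with equal readers is about 80% per measurement, and a device with ratio 1.5 is accepted in about 9% of trials. The excess over the nominal 2.5% arises because error in the raters' mean is shared by both readers. The ratio seen is √((2.25 + v)/(1 + v)), which is 1.44, 1.41 and 1.39 for v = 1/6, 1/4 and 1/3.

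**The case against.** **The ratio of 1.5 is not in the documents.** This stands. It would put about 8% of device readings outside the limits, whereas Table 3 pools to 1.8% against 0.8%. Under the same normal model those shares correspond to z = 2.37 and 2.63, an observed ratio of 2.63/2.37 = 1.11, or about 1.1 to 1.2 once error in the raters' mean is allowed for. A reader might infer that Ligence Heart is 1.5 times less precise. Table 3 does not support that on average, although single measurements could differ.

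**The rate is per measurement.** A reader might infer that the overall claim would survive in six of ten trials. It would not: if the 21 measurements were independent, 0.59^21 is about 0.00002, and with correlation the figure lies somewhere between that and 0.59.

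**The 1.3% is not an information fraction.** A reader might infer that the decision uses about 1% of the information. The paired absolute-error test needs about 30 studies to match the in/out test at 58, so at ratio 1.5 the in/out test keeps roughly half (30/58 = 0.52).

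**Larger differences are detected.** At ratio 1.75 the in/out test fails the device in about 74% of trials, and at 1.25 the absolute-error test also misses it in most. It would be too strong to say that a clearly less precise device usually goes undetected.

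**Other continuous data are shown, and the limit is inferred.** Correlations and individual readings appear in 15.2, but none enters the pass rule, and correlation does not measure absolute error. That the limit in 15.2 is MDC follows from 12.5.2 and is an inference; the conclusion survives the calibrated limit above.

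**The pass rule is the larger defect.** This also stands. With p > 0.05 kept, absolute errors still pass the 1.5-times device about one time in three. Most of the protection comes from a margin.

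**Conclusion.** The point holds per measurement. The in/out reduction, combined with passing on p > 0.05 or undefined, is a weak basis for non-inferior accuracy: 7 of 21 passes carry no test result and the other 14 rest on 1 to 4 events. At an assumed SD ratio of 1.5 the rule passes a device about 60% of the time, against about 33% for the same rule on absolute errors and about 9% with a CI and an assumed margin of 1.5. These figures rest on normal, unbiased errors, on MDC being the limit, and on SD ratios that are illustrative. They say how well the rule discriminates. They do not show that Ligence Heart is less accurate than the cardiologist, nor give a pass rate for all 21 measurements together.

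**What to change.** In 12.5.2 and Table 3, compare for each measurement |Ligence Heart − raters' mean| with |fourth cardiologist − raters' mean| on the same studies, as a paired difference or ratio with a 95% CI (a paired bootstrap would serve). Claim non-inferiority only where the CI excludes a margin that the sponsor justifies. Stop using p > 0.05 or undefined as the pass rule, and keep the share inside MDC as descriptive.

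State that error in the raters' mean pulls the ratio toward 1, so that a true 1.5 appears as about 1.4. Either set the margin on that attenuated scale or correct for it with the ANOVA variance components already planned in 12.5.1. Name the limit used in 15.2. Because the results are known, label the work a post hoc re-analysis.

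Cost: no new readings are needed. The downside is real. At about 80% power per measurement, an equivalent device would be expected to miss on 0.2 × 21, or about 4, of the measurements, so several passes may become inconclusive. A tighter margin costs more: at 1.25, power with equal readers falls to about 38%.

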## **5.2 Objectives**

### **5.2.1 Primary Objectives**

UAB Ligence	Clinical Investigation Report	2021-04-09
		Rev: 1.0

4. Manual measurement analysis: To calculate the reliability of Ligence Heart manual functions that are used to perform echocardiographic measurements comparing it with the manual measurements performed with other CE marked state-of-the-art medical image viewers.
5. Automatic measurement analysis: To compare Ligence Heart automatic measurements accuracy, variance, and error rate with human physicians in real clinical setting.
6. Time used comparison: To compare Ligence Heart automatic measurement tool execution time with the time it takes a physician to perform the measurements manually.

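### Section 15.2 reads the Table 3 p-values as showing no difference in variation, but they compare the share of studies in agreement with the reference raters, and seven rows have no p-value

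*Protocol*

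**What the plan says.** The automatic-measurement objective (number 2 in the synopsis, number 5 in section 5.2.1) names variance separately from accuracy: "To compare Ligence Heart automatic measurements accuracy, variance, and error rate with human physicians in real clinical setting".

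Section 15.2 defines the performance measure: "NRG performance was evaluated by calculating the number of measurements of each type that were in the limits of variation". It then concludes "There was no significant difference in variation between Ligence Heart and FC", with p > 0.05. Under the footnote to Table 3, a measurement passes if p exceeds 0.05 or is undefined, which is said to mean that "there is no significant difference in variation between Ligence Heart and FC measurements". The footnote also explains that p is undefined where both readers agree with ORG in every study.

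Section 16.2 describes the same analysis differently, with "accuracy calculated as the number of times measurements fell within acceptable variation range", and adds: "Non-inferiority of automatic measurements accuracy to a cardiologist was established by conducting the t-test". It does not say whether the t-test was paired. Section 15.2 states that FC and Ligence Heart measured the same 58 studies.

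**The concern.** One column of p-values is given two meanings: a comparison of variation in section 15.2 and the footnote, and a comparison of accuracy (a count inside limits) in section 16.2. Only one can be right. A share of studies inside a limit is not a measure of spread. Two readers can both fall inside wide limits in nearly every study and still scatter quite differently around the reference.

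Because variance is a named part of a primary objective, a reader could take the sentence as evidence that the device's scatter matches a cardiologist's. For seven measurements the statement rests on no test result at all.

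**Working it through.** **Inputs.** The percentages and N in Table 3, converted to counts. For RAMAD, 96.3% and 98.15% of 54 are 52 and 53 studies.

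**Reproducing the p-values.** Code each study 1 (in agreement) or 0. With share p, the sample variance is s² = p(1 − p)·n/(n − 1). The two-sample statistic is t = (p_LH − p_FC)/√[(s²_LH + s²_FC)/n] on 2n − 2 degrees of freedom.

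- RAMAD: difference 52/54 − 53/54 = −0.01852; variances 0.03634 and 0.01852; standard error √(0.05486/54) = 0.03187; t = −0.581; p = 0.5625. Printed: 0.56.
- LAV4A: difference 55/56 − 53/56 = 0.03571; variances 0.01786 and 0.05162; standard error √(0.06948/56) = 0.03522; t = 1.014; p = 0.313. Printed: 0.31.

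| Measurement | LH | FC | n | Recomputed p | Printed p |
|---|---|---|---|---|---|
| RAMAD | 52 | 53 | 54 | 0.5625 | 0.56 |
| AoA | 57 | 57 | 58 | 1 | 1 |
| AAo | 57 | 58 | 58 | 0.319 | 0.32 |
| LAD | 55 | 58 | 58 | 0.081 | 0.08 |
| LAV4A | 55 | 53 | 56 | 0.313 | 0.31 |
| LVPWd | 56 | 58 | 58 | 0.156 | 0.16 |
| LVEDV4A | 55 | 56 | 56 | 0.320 | 0.32 |
| LVEDV2A, LVESV2A | 52 | 54 | 54 | 0.156 | 0.16 |
| RAA | 51 | 53 | 54 | 0.313 | 0.31 |
| RVB | 54 | 54 | 55 | 1 | 1 |
| RVM | 55 | 52 | 55 | 0.080 | 0.08 |
| RVEDA, RVESA | 54 | 55 | 55 | 0.320 | 0.32 |

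All 14 match, and the Welch form matches too.

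**Alternatives tried.** Each fails in at least one row:

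- Paired t gives 0.57 or 0.32 for RAMAD (depending on whether the two readers failed in the same study), and 0.32 or 0.16 for LAV4A and RAA.
- McNemar chi-square gives 0.32 or 0.16 for LAV4A and RAA.
- The pooled z-test gives 0.15 for LVPWd.
- The unpooled z-test gives 0.31 for AAo.
- Fisher's exact test gives 1.0 for RAMAD.

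That the test was unpaired is therefore an inference from the numbers.

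**Rows without a p-value.** AoS, STJ, IVSd, LVEDD, LVESD, LVESV4A and RVOTPD: 7 of 21.

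**Respecting the pairing.** Exact McNemar gives 0.25 for LAD and RVM; 0.50 for LVPWd, LVEDV2A and LVESV2A; 0.50 to 0.625 for LAV4A and RAA; and 1.0 for the other defined rows. No row changes its Pass under the report's own rule.

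**How poorly agreement stands in for scatter (illustration).** Assumptions: n = 58; normal, unbiased differences from the ORG mean; limits at 2.45 SD of FC's differences, which gives FC 98.6% agreement; correlation 0 to 0.5 between the two readers' differences. The second column is the Pitman-Morgan paired variance test on the continuous differences.

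| True SD ratio, LH to FC | Agreement t-test rejects | Pitman-Morgan rejects |
|---|---|---|
| 1.3 | 20–23% | 50–63% |
| 1.5 | 54–56% | 85–94% |

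With equal scatter the agreement test rejects in under 1% of data sets and is undefined in 18 to 21%.

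**The case against.** The strongest reply is that variation is shorthand. Section 15.2 is about accuracy; the limits of variation are defined just before the sentence at issue; Table 3's title and columns speak of agreement; the footnote ties Pass to accuracy; and section 16.2 names the quantity and the test openly. This is a fair account of how the wording may have arisen. It does not make the sentence or the footnote correct as written, given that variance is named separately in the objective.

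Second, variability is reported elsewhere. The only variability hypothesis in section 12.1 concerns intra-rater variability, and section 15.3 with Table 4 addresses it. That stands, and it would be wrong to say that the report is silent on variability. But section 15.3 compares run-to-run correlation with the ORG raters and leaves FC out. The device scores 1 because its output is fixed by its input, which says nothing about its scatter around the reference. It is also true that section 12.5.2 plans no comparison of SDs between Ligence Heart and FC, so equating variance in the objective with that ratio is one reasonable reading and not the document's own definition.

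Third, the blank rows are disclosed, and the observed difference in agreement there is zero. This stands for agreement; it does not support a statement about variation.

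Fourth, a reader might infer that the device is more variable than FC, or that ignoring the pairing produced the Pass results. The documents support neither. Individual values are not available, no SD can be computed, and the simulation rests on assumed scatter ratios.

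**Conclusion.** The point holds as an error of interpretation. The statement about variation in section 15.2 and the footnote to Table 3 is attached to p-values that compare proportions of studies in agreement, and it extends to seven measurements with no p-value. No comparison of Ligence Heart and FC scatter around the ORG mean is reported. No printed percentage, p-value or Pass changes.

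The identification of the test rests on all 14 values matching and on the failure of the alternatives tried; unpaired is inferred. The rejection rates are illustrative and depend on normal, unbiased differences and an assumed limit. Whether p > 0.05 without a margin can establish non-inferiority is a separate question.

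**What to change.** In section 15.2 and the footnote to Table 3, replace the reference to a difference in variation with a difference in the proportion of studies in agreement with ORG. Report undefined p-values as not computable, and do not describe them as showing no significant difference.

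If a statement on the variance part of the objective is to be kept, support it. For each of the 21 measurements, on the studies that both readers measured, give the ratio of the SD of (Ligence Heart minus ORG mean) to the SD of (FC minus ORG mean), with a 95% CI from a bootstrap over studies. Use Pitman-Morgan only if the differences are close to normal: with equal scatter and t-distributed differences on 5 degrees of freedom (an assumption, n = 58), it rejected about 15% of the time instead of 5%. Present the ratios as estimates and note the multiplicity over 21 measurements.

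A paired comparison of agreement suits the design and can replace the t-test without altering any Pass.

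The cost is two wording changes and some re-analysis of values already collected. The downside is that some measurements may show less favourable device scatter than the present text suggests.

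### Table 3 measures automatic accuracy only in studies where Ligence Heart returned a value, yet non-inferiority is concluded without that condition

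*Protocol*

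**What the plan says.** The second primary objective (section 5.2.1) is "To compare Ligence Heart automatic measurements accuracy, variance, and error rate with human physicians in real clinical setting". Section 15.2 says of the two readers compared with the three original raters (ORG): "The new rater group (NRG) consisting of a fourth cardiologist (FC) and Ligence Heart performed measurements in the same 58 studies". It gives the outcome as follows: "NRG performance was evaluated by calculating the number of measurements of each type that were in the limits of variation".

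On missing device values, section 15.2 states that "Ligence Heart discarded 2-4 studies in RAMAD, LAV4A, LVEDV4A, LVESV4A, LVEDV2A, LVESV2A, RVEDA and RVESA due to insufficient quality scores of automatic predictions", which names 8 measurements. Section 16.2 says that "Ligence Heart automatic functionalities did not return a value for at least one study in 11 measurements", and Table 3 agrees with 11: it adds RAA (4 studies), RVB (3) and RVM (3).

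The pass rule is in the note to Table 3: "In order for the automated measurements to pass, a P value of > 0.05 or undefined is required". Section 16.2 repeats it: "Non-inferiority of automatic measurements accuracy to a cardiologist was established by conducting the t-test and assuring p-values are" above 0.05. All 21 measurements are marked as passing.

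For the device's worst measurement the text says "The lowest number of studies in agreement with ORG was 93.1% in RAA", while the RAA row of Table 3 gives 94.44%.

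**The concern.** Whether a study enters a row of Table 3 depends on the output of the device under test. Where its confidence filter withheld a value, FC's reading of that study was set aside too. The table therefore answers the question of how often the device agrees with ORG when it gives a value.

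The claims are wider than that. Section 15.2 concludes non-inferior accuracy for all automatic measurements, section 16.2 says that all passed and describes the validation as end to end, and its closing summary repeats the claim without qualification. Section 16.2 attributes non-return to the steps that end-to-end validation is meant to cover: classification, cardiac phase or cycle detection, and measurement prediction. Section 16.4 does not list non-return as a limitation. At stake is whether the main accuracy claim holds for a study put through the device, or only for a study in which the device produced a result.

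**Working it through.** **Inputs.** Percentages, N and filtered counts come from Table 3; the 58 studies from section 15.2; the test and pass rule from section 16.2 and the note to Table 3. Counts are percentage × N.

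**1. FC was also cut to the reduced set.** FC's 98.15%, 94.64%, 94.55% and 98.18% are 53/54, 53/56, 52/55 and 54/55. Out of 58 the nearest possible values are 57/58 = 98.28% and 55/58 = 94.83%, so these figures cannot come from 58 studies.

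**2. Extent of non-return.** In Table 3 order: 4+2+2+2+4+4+4+3+3+3+3 = 34 values. 34/(21 × 58) = 34/1,218 = 2.8%. Per measurement, with exact (Clopper-Pearson) 95% intervals:
- 4/58 = 6.9% (1.9 to 16.7)
- 3/58 = 5.2% (1.1 to 14.4)
- 2/58 = 3.4% (0.4 to 11.9)

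**3. Reproducing Table 3.** Score each study 1 (in agreement) or 0 and use a two-sided unpaired t-test: t = (p₂ − p₁)/√(s₁²/n + s₂²/n), with s² = p(1 − p)n/(n − 1). For LVEDV2A, p₁ = 52/54, s₁² = 0.0363 and s₂² = 0, so t = 0.0370/√(0.0363/54) = 1.43 on 106 df and p = 0.16, as stated. All 14 defined p-values in the table reproduce to two decimals this way.

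**4. All 58 studies, non-return counted as not in agreement.** The device's numerator stays the same and its denominator becomes 58. FC's results in the dropped studies are not reported, so the range is shown. For LVEDV2A with FC in agreement on all four dropped studies: p₁ = 52/58, s₁² = 0.0944, t = 0.1034/√(0.0944/58) = 2.56 on 114 df, p = 0.012.

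| Measurement | Device, Table 3 | Device, of 58 | p stated | p if FC agreed on all dropped | p if FC missed one dropped |
|---|---|---|---|---|---|
| LVEDV2A, LVESV2A (each) | 52/54 | 89.7% | 0.16 | 0.012 | 0.052 |
| RAA | 51/54 | 87.9% | 0.31 | 0.028 | 0.084 |
| RVEDA, RVESA (each) | 54/55 | 93.1% | 0.32 | 0.042 | 0.173 |
| RAMAD | 52/54 | 89.7% | 0.56 | 0.052 | 0.145 |
| LVEDV4A | 55/56 | 94.8% | 0.32 | 0.081 | 0.313 |
| LVESV4A | 56/56 | 96.6% | undefined | 0.156 | 0.563 |
| RVB | 54/55 | 93.1% | 1 | 0.173 | 0.406 |
| LAV4A | 55/56 | 94.8% | 0.31 | 1.0 | 0.700 |
| RVM | 55/55 | 94.8% | 0.08 | 1.0 | 0.700 |

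Five Pass results change if FC agreed on every dropped study. None changes if FC missed one in each row.

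**5. Other tests, with FC in agreement on all dropped studies.** Fisher's exact test changes 2 (LVEDV2A and LVESV2A, p = 0.027; RAA 0.061). Exact McNemar changes the same 2 (p = 0.031), plus RAA if FC's single miss there was also a device miss (0.031; otherwise 0.070). A paired t-test changes 5, or 6 if FC's single RAMAD miss was also a device miss (0.024).

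**6. The RAA conflict.** No count out of 54 gives 93.1% (50/54 = 92.59%, 51/54 = 94.44%), but 54/58 = 93.10%. If 54/58 is what the text means, it fits Table 3's 51/54 only if 3 of the 4 filtered values existed and agreed. The 51/58 used above would then be wrong, and 54/58 against 57/58 gives p = 0.173.

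**The case against.** The strongest reply is that a withheld value is not a wrong value. Section 12.5.2 defines the endpoint as the difference between the automated measurement and the raters' mean, which does not exist without a measurement. Section 16.2 presents the filter as a safety feature, and section 4.3 requires a clinician to review and approve the automatic results. Counting non-return as disagreement is thus one choice of estimand. This stands: it belongs beside conditional accuracy and the return rate, not in place of them.

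The exclusion is also disclosed. Table 3 gives the filtered count per row and section 16.2 discusses it. That is fair, but section 16.2 defends the exclusion only by saying that enough studies remained for power. Power does not answer selection by the device's own output, and disclosure does not narrow the unconditional conclusion.

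A reader might infer that several Pass results would certainly fail, or that the filter removed the hardest studies. The documents support neither. Every change requires FC to have agreed on all the dropped studies of that row, which is not reported. The documents say only that the device's predictions missed its quality thresholds. If those studies were hard for everyone, FC misses become more likely and the changes disappear. That section 12.5.2 has no rule for missing device values is not held against the document, since a separate analysis plan may contain one.

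**Conclusion.** The point holds in this form: for 11 of 21 measurements Table 3 reports accuracy conditional on a returned value, and the conclusions drop the condition. This rests on the table's own denominators and needs no assumption about FC.

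The size of the effect on pass results is uncertain. With the document's test and rule it is 0 to 5 of 21, governed by FC's unreported results in the dropped studies; the RAA entry also depends on which RAA figure is right. It would be wrong to read even five changes as evidence that the device is inferior. A rule of p > 0.05 with no margin cannot establish non-inferiority, and crossing it by a few studies shows only that the result is fragile.

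The two contradictions (RAA 93.1% against 94.44%; 8 against 11 affected measurements) need correction whatever estimand is chosen.

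**What to change.** - Score FC on all 58 studies for every measurement, and report FC's results in the studies where the device returned nothing.
- Report two analyses side by side: all 58 studies with non-return counted as not in agreement, and agreement among returned values, labelled *when a value is returned*.
- Give the non-return rate per measurement with an exact 95% interval, under the error-rate part of the objective in section 5.2.1.
- Restrict the non-inferiority statements in sections 15.2 and 16.2 to returned values unless the all-58 analysis supports them, and add non-return to the limitations in section 16.4.
- Reconcile RAA 93.1% in the text of section 15.2 with 94.44% in Table 3, and the 8 measurements listed there with the 11 in Table 3 and section 16.2.

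**Cost.** This is re-tabulation of readings that section 15.2 says exist for all 58 studies, though FC's completeness per measurement is not reported and should be confirmed. In the all-58 analysis, reported device agreement falls for 11 measurements.
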